9.2. Statistical Method

[figure not shown]
9.2.1. HZ incidence

- For the primary analysis of HZ incidence, first confirmed HZ episode will be considered.
- The HZ onset date is the earlier of the following two events: 1) the HZ rash start date; or 2) the date on which pain/itching or abnormal sensation at the site of a subsequent HZ rash is first noted.
- A suspected case of HZ can be confirmed by GSK in two ways:
 - **By PCR:** Rash lesion samples will be collected from subjects clinically diagnosed as having a suspected case of HZ. The samples will be transferred to GSK or a validated laboratory designated by GSK Biologicals and analyzed using standardized and validated procedures for laboratory diagnosis of HZ by PCR (see Section 12.2 of the protocol).
 - **By the HZ Ascertainment Committee (HZAC):** All suspected HZ cases will be referred to the HZAC. The HZAC will classify all referred cases as either “HZ” or “not HZ” or “not able to decide” (see Section 12.2 of the protocol). The HZAC classification will serve as the final case definition only when the case cannot be confirmed or excluded by PCR. Therefore, definitive PCR results, when available, will determine the final HZ case assignment. In such cases, the HZAC classification will not contribute to HZ case determination decision
- For a given subject and for HZ episode, missing or non-evaluable measurements will not be imputed for the primary analysis. The missing endpoint and censoring are considered to occur independently, and the pattern being either Missing Completely At Random (MCAR) or Missing At Random (MAR) only.
- For HZ analysis, due to the algorithm used and taking into account both laboratory and HZAC results, no imputation and no sensitivity analysis for missing data will be performed.
- The “follow-up time at risk” for confirmed HZ is expressed in days and is computed according to the following rules:
 - The start date of the follow-up time (start) will be computed as follows:
 - From the dose 1 administration date for the analysis on the ES;
 - From 30 days post-dose 2 date for the analysis on the mES.
 - The end date of the follow-up time (stop) will be computed as follows:
 - Date of the last visit/contact for subjects who did not have an event;
 - Last contact date for subjects dropped out of the study, if not preceded by an event;

- Date of the event
- Date of HZ and/or VZV vaccination outside the study, if not preceded by an event
- The follow-up time at risk is computed using the following formula:
 - **stop – start +1.**

The **time at risk** will be expressed in Person-Year and derived from the follow up time (follow up time in days/365.25).

CCI

9.2.3. Safety

- For the analysis of HZ related complications/unsolicited AEs/SAEs/pIMDs/concomitant medication, all vaccinated subjects will be considered and subjects who did not report an event will be considered as subjects without an event.
- AEs that need to be reported as pIMDs are listed in Table 23 of the protocol. *The table presenting pIMDs, will also include the AEs considered as pIMDs as per MedDRA dictionary.*
- Assessment of intensity for solicited local and general AEs will be done separately as per GSK scale and Chinese scale. From an analysis perspective, the intensity of nausea, vomiting and diarrhoea will be presented separately as per the guidelines of Chinese authorities. In addition, as per GSK standard grading, the solicited general AEs of nausea, vomiting, diarrhoea and/or abdominal pain will be presented collectively as “gastrointestinal symptoms”.

For analysis as per GSK standard grading, the maximum intensity of any one of these solicited general AEs (i.e. nausea, vomiting and diarrhoea **and abdominal pain**) reported by a subject will be attributed as maximum intensity of “gastrointestinal symptoms” for that subject. Maximum of grade 3 and 4 will be considered as grade 3 **for all applicable solicited symptoms (not only gastrointestinal symptoms) in GSK standard grading table.**

The intensity of the following solicited AEs will be assessed as described below:

Table 3 Intensity scales for solicited symptoms in adults

Adults		
Adverse Event	Intensity grade	Parameter
Pain at injection site	0	None
	1	Mild: Do not influence or do slightly influence limb activities.
	2	Moderate Influence limb activities.
	3	Severe: Influence daily life.
	4	Lose the basic selfcare ability, or hospitalization
Redness at injection site		Record greatest surface diameter in mm
Swelling at injection site		Record greatest surface diameter in mm
Temperature*		Record temperature in °C (with 1 decimal)
Headache	0	Normal
	1	Mild: Headache that is easily tolerated
	2	Moderate: Headache that interferes with normal activity
	3	Severe: Headache that prevents normal activity
	4	Refractory; require emergency presentation or hospitalization
Fatigue	0	Normal
	1	Mild: Fatigue that is easily tolerated
	2	Moderate: Fatigue that interferes with normal activity
	3	Severe: Fatigue that prevents normal activity
	4	Emergency presentation or hospitalization
Gastrointestinal symptom (Diarrhea)	0	Normal
	1	Slight or transient, 3-4 times/day, stool with abnormal properties, or slight diarrhea persisting for not more than 1 week

Adults		
Adverse Event	Intensity grade	Parameter
	2	Moderate or persistent, 5-7 times/days, stool with abnormal properties, or diarrhea >1 week
	3	>7 times/day, stool with abnormal properties, or bloody diarrhea, orthostatic hypotension, electrolyte imbalance, and requiring intravenous fluid >2 L
	4	Hypotensive shock, requiring hospitalization for treatment
Gastrointestinal symptom (Nausea)	0	Normal
	1	Transient (<24 h) or intermittent, while food intake basically normal
	2	Persistent nausea, leading to decreased food intake (24-48 h)
	3	Persistent nausea, leading to little food intake (>48 h) or require intravenous fluid infusion
	4	Life-threatening (such as hypotensive shock)
Gastrointestinal symptom (Vomiting)	0	Normal
	1	1-2 times/24 h and do not influence activities
	2	3-5 times/24 h or activities restricted
	3	>6 times within 24 h or require intravenous fluid infusion
	4	Due to hypotension, require hospitalization or nutrition by other routes
Gastrointestinal symptom (Abdominal pain)	0	Normal
	1	Mild: Gastrointestinal symptoms that are easily tolerated
	2	Moderate: Gastrointestinal symptoms that interfere with normal activity
	3	Severe: Gastrointestinal symptoms that prevent normal activity
Myalgia	0	None
	1	Mild: Myalgia that is easily tolerated
	2	Moderate: Myalgia that interferes with normal activity
	3	Severe: Myalgia that prevents normal activity

* For this study, fever is defined as temperature $\geq 37.3^{\circ}\text{C}$ as per guidelines from the Chinese authorities for axillary measurement. The preferred location for measuring temperature in this study will be the axilla.

The maximum intensity of local injection site redness/swelling will be scored at GSK using GSK's standard grading scale (based on the US Food and Drug Administration (FDA) guidelines [FDA, 2007]) and the guidelines of grading standards for AEs set by the Chinese authorities as follows.

Grade	GSK standard grading scale	Grading scale defined by Chinese authorities
0	< 20 mm diameter	Absent
1	≥ 20 mm to ≤ 50 mm diameter	25 mm to <50 mm
2	> 50 mm to ≤ 100 mm diameter	50 mm to <100 mm
3	> 100 mm diameter	≥ 100 mm
4	Not defined	Abscess, exfoliative dermatitis, and dermis or deep tissue necrosis*

***The solicited symptom diary card doesn't allow to choose grade 4 swelling or redness. Per team agreement, the grade 4 of swelling and redness will be identified when the below Preferred Terms (from MedDRA version 25.0) are reported as unsolicited adverse events within or ongoing 7 days post each dose:**

- **Dermatitis exfoliative**
- **Necrosis**

- ***Skin necrosis***
- ***Soft tissue necrosis***
- ***Abscess***
- ***Abscess sterile***
- ***Abscess limb***
- ***Abscess soft tissue***

Fever will be graded as:

Grade	GSK standard grading scale	Grading scale defined by Chinese authorities (for axillary measurement)
0	<38.0°C	<37.3°C
1	≥38.0°C –≤38.5°C	37.3°C –<38°C
2	>38.5°C –≤39.0°C	38.0°C -<38.5°C
3	>39.0°C	38.5°C - <39.5°C
4	Not defined	≥ 39.5°C

The preferred location for measuring temperature in this study will be the axilla. If temperature is measured by other routes (such as oral or rectal), fever grading as per GSK scale will remain the same irrespective of route of measurement. For the grading scale as per Chinese authorities, the following conversion will be used:

- Axillary temperature = Oral temperature minus 0.2°C;
- Axillary temperature = Rectal temperature minus 0.5°C.
- ***Axillary temperature = Tympanic membrane temperature***
- ***For the duration of solicited adverse event within the solicited symptom follow-up or total duration, the unknown or missing end date will not be imputed.***
- The definition of HZ related complication is described in section 12.5.2 of the protocol and is presented below:-

Post-herpetic neuralgia	PHN is defined by the presence of HZ-associated severe pain persisting or appearing more than 90 days after onset of the HZ rash.
Disseminated disease	Defined as ≥ 6 HZ lesions clearly outside the primary dermatome as per the investigator's judgment.
Ophthalmic disease	Defined as HZ affecting any eye structure as per the investigator's judgment.

Neurologic disease	Defined as cranial or peripheral nerve palsies, myelitis, meningoencephalitis, stroke, etc. that is temporally associated with an episode of HZ and, in the opinion of the investigator, is caused directly by VZV infection arising from the HZ episode.
Visceral disease	Defined as an abnormality of one or more internal organs (e.g., hepatitis, pneumonitis, gastroenteritis, etc.) that is temporally associated with an episode of HZ and, in the opinion of the investigator, is caused directly by VZV infection arising from the HZ episode
HZ vasculitis	Vasculopathy or vasculitis (based on clinical, laboratory or radiologic findings) that is temporally associated with an episode of HZ and, in the opinion of the investigator, is caused directly by the VZV infection arising from the HZ episode.
Stroke	
A diagnosis of stroke requires that criteria 1, 2 and 3 are fulfilled or criteria 1 and 4 and in the opinion of the investigator is temporally associated with an episode of HZ
 
Criterion 1: Rapid onset of localizing neurological deficit and/or change in level of consciousness;
 
Criterion 2: Localizing neurological deficit or change in level of consciousness that lasts greater than 24 hours;
 
Criterion 3: No other cerebral process, peripheral lesion, or other disorder is the cause of the localizing neurological deficit or change in level of consciousness;
 
Criterion 4: Computerized Tomography (CT) scan or Magnetic Resonance Imaging (MRI) scan evidence of an acute thrombotic or hemorrhagic lesion

- *A specific COVID-19 eCRF page is used to collect any event related to COVID-19 pandemic. Input from local regulatory, local medical affairs and sites was provided to define pandemic measures periods at each site. Start date of pandemic measure period will be considered first day of month and end date of pandemic measure period will be considered as last day of month.*

Location	Center	First subject first visit date at Center	Start date of pandemic measure period	End date of pandemic measure period	Reason/s for pandemic measure period
Shanghai	248981	14-May-21	Mar21	May21	Strong recommendation of mass vaccination of Covid-19 vaccines to wide population. Isolated cases in country lack of resources that delay the Study start
			Mar22	Jun22	Covid-19 outbreak in Shanghai High business, public life and health impact Widespread disease in region and community Citywide static management lack of resources that lead to miss of month phone contact
			Oct22	Nov22	Province/Partial control to prevent Covid-19 Isolated cases in country Lack of resources that impact data entry
			Nov22	Jan23	High business public life and health impact Widespread disease in country Sustained community spread in geographic area local to GSK community Public health service capacity exceeded lack of resources that impact data entry
Shanghai	248302	21-Jul-21	Mar21	May21	Strong recommendation of mass vaccination of Covid-19 vaccines to wide population. Isolated cases in country lack of resources that delay the Study start

Location	Center	First subject first visit date at Center	Start date of pandemic measure period	End date of pandemic measure period	Reason/s for pandemic measure period
			Mar22	Jun22	Covid-19 outbreak in Shanghai High business, public life and health impact Widespread disease in region and community Citywide static management Lack of resources that impact data entry
			Oct22	Nov22	Province/Partial control to prevent Covid-19 Isolated cases in country Lack of resources that impact data entry
			Nov22	Jan23	High business public life and health impact Widespread disease in country Sustained community spread in geographic area local to GSK community Public health service capacity exceeded lack of resources that impact data entry
			Mar21	May21	Strong recommendation of mass vaccination of Covid-19 vaccines to wide population. Isolated cases in country lack of resources that delay the Study start
248303	15-Jul-21	Mar22	Jun22		Covid-19 outbreak in Shanghai High business, public life and health impact Widespread disease in region and community Citywide static management Lack of resources that impact data entry

CONFIDENTIAL

212884 (ZOSTER-076)
Statistical Analysis Plan Amendment 1

Location	Center	First subject first visit date at Center	Start date of pandemic measure period	End date of pandemic measure period	Reason/s for pandemic measure period
			Oct22	Nov22	
Province/Partial control to prevent Covid-19
 
Isolated cases in country
 
Lack of resources that impact data entry

			Nov22	Jan23	
High business public life and health impact
 
Widespread disease in country
 
Sustained community spread in geographic area local to GSK community
 
Public health service capacity exceeded
 
lack of resources that impact data entry

			Mar21	May21	
Strong recommendation of mass vaccination of Covid-19 vaccines to wide population.
 
Isolated cases in country
 
lack of resources that delay the Study start

			Mar22	Jun22	
Covid-19 outbreak in Shanghai
 
High business, public life and health impact
 
Widespread disease in region and community
 
Citywide static management
 
Lack of resources that impact data entry

			Oct22	Nov22	
Province/Partial control to prevent Covid-19
 
Isolated cases in country
 
Lack of resources that impact data entry

247421	06-Jun-21				

Location	Center	First subject first visit date at Center	Start date of pandemic measure period	End date of pandemic measure period	Reason/s for pandemic measure period
			Nov22	Jan23	High business public life and health impact Widespread disease in country Sustained community spread in geographic area local to GSK community Public health service capacity exceeded lack of resources that impact data entry
			Mar21	Jul21	Strong recommendation of mass vaccination of Covid-19 vaccines to wide population. Isolated cases in country lack of resources that delay the Study start
			Jul21	Aug21	Covid19 outbreak in Nanjing city and Jiangsu province Province/Partial control to prevent Covid-19 Lack of resources that delay the study start
			Mar22	Jun22	Covid-19 outbreak in Shanghai Province/Partial control to prevent Covid-19 Lack of resources that delay the data entry
			Oct22	Nov22	Province/Partial control to prevent Covid-19 Isolated cases in country Lack of resources that delay the data entry
					High business public life and health impact Widespread disease in country Sustained community spread in geographic area
Lianshui	247564	11-Sep-21	Nov22	Jan23	

Location	Center	First subject first visit date at Center	Start date of pandemic measure period	End date of pandemic measure period	Reason/s for pandemic measure period
					local to GSK community Public health service capacity exceeded lack of resources that impact data entry
			Mar21	Jul21	Strong recommendation of mass vaccination of Covid-19 vaccines to wide population. Isolated cases in country lack of resources that delay the Study start
			Jul21	Aug21	Covid19 outbreak in Nanjing city and Jiangsu province Province/Partial control to prevent Covid-19 Lack of resources that delay the study start
			Mar22	Jun22	Covid-19 outbreak in Shanghai Province/Partial control to prevent Covid-19 Lack of resources that impact the data entry
			Jul22	Aug22	Covid-19 epidemic in Ganyu citywide static management Partial control and travel restrictions to prevent and control Covid-19 lack of resources that impact the data entry
Ganyu	248595	15-Sep-21	Oct22	Nov22	Province/Partial control to prevent Covid-19 Isolated cases in country Lack of resources that impact the data entry

Location	Center	First subject first visit date at Center	Start date of pandemic measure period	End date of pandemic measure period	Reason/s for pandemic measure period
			Nov22	Jan23	High business public life and health impact Widespread disease in country Sustained community spread in geographic area local to GSK community Public health service capacity exceeded lack of resources that impact data entry

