	4	Hypotensive shock, requiring hospitalization for treatment
Gastrointestinal symptom (Nausea)	0	Normal
	1	Transient (<24 h) or intermittent, while food intake basically normal
	2	Persistent nausea, leading to decreased food intake (24-48 h)
	3	Persistent nausea, leading to little food intake (>48 h) or require intravenous fluid infusion
	4	Life-threatening (such as hypotensive shock)
Gastrointestinal symptom (Vomiting)	0	Normal
	1	1-2 times/24 h and do not influence activities
	2	3-5 times/24 h or activities restricted
	3	>6 times within 24 h or require intravenous fluid infusion
	4	Due to hypotension, require hospitalization or nutrition by other routes
Gastrointestinal symptom (Abdominal pain)	0	Normal
	1	Mild: Gastrointestinal symptoms that are easily tolerated
	2	Moderate: Gastrointestinal symptoms that interfere with normal activity
	3	Severe: Gastrointestinal symptoms that prevent normal activity
Myalgia	0	None
	1	Mild: Myalgia that is easily tolerated
	2	Moderate: Myalgia that interferes with normal activity
	3	Severe: Myalgia that prevents normal activity
	4	Emergency presentation or hospitalization

Adults		
Adverse Event	Intensity grade	Parameter
Shivering	0	None
	1	Shivering that is easily tolerated
	2	Shivering that interferes with normal activity
	3	Shivering that prevents normal activity

* For this study, fever is defined as temperature $\geq 37.3^{\circ}\text{C}$ as per guidelines from the Chinese authorities for axillary measurement. The preferred location for measuring temperature in this study will be the axilla.

The maximum intensity of local injection site redness/swelling will be scored at GSK using GSK's standard grading scale (based on the US Food and Drug Administration (FDA) guidelines [FDA, 2007]) and the guidelines of grading standards for AEs set by the Chinese authorities as follows.

GSK standard grading scale		Grading scale defined by Chinese authorities
0 :	< 20 mm diameter	Absent
1 :	$\geq 20 \text{ mm to } \leq 50 \text{ mm diameter}$	25 mm to <50 mm
2 :	$> 50 \text{ mm to } \leq 100 \text{ mm diameter}$	50 mm to <100 mm
3 :	$> 100 \text{ mm diameter}$	>100 mm
4	Not defined	Abscess, exfoliative dermatitis, and dermis or deep tissue necrosis

Fever will be graded as:

GSK standard grading scale		Grading scale defined by Chinese authorities (for axillary measurement)
0 :	<38.0°C	<37.3°C

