8. CHANGES TO THE PROTOCOL DEFINED STATISTICAL ANALYSIS

Following is the change from protocol defined statistical analysis:-

- Fatal SAEs will not be tabulated using the date of death within the same time periods.
- **CC1**
- *Grade 3 for redness/swelling will be defined as redness/swelling with diameter ≥ 100 mm in Chinese scale*
- *Preferred Terms to identify Grade 4 for swelling and redness have been added*
- *The analysis on at least 1 local AE (solicited and unsolicited; solicited only) with at least 1 general AE (solicited and unsolicited; solicited only) and with any AE (solicited and unsolicited; solicited only) during the solicited follow-up period with causal relationship with vaccine and AE rated as at least grade 3 according to GSK and Chinese scale will not be performed.*

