10.1.2.3.2. Studies with paper diaries

For studies using paper diaries which have questions in the CRF indicating the presence or absence of solicited events, the following rules are applicable.

- *Denominators for the summary of administration site (or systemic) solicited events will be calculated using the number of participants who respond "Yes" or "No" to at least one occurrence of the specific administration site (or systemic) solicited event. If there are at least 1 non-missing value of temperature from day 1 to day 7 post vaccination, that occurrence will be counted as well in the denominator of systemic solicited events.*
- When a specific solicited event is marked as having not occurred following a specific study dose (i.e. SDTM CE.CEOCCUR=N for the specified post-dose period for the event in question), all daily measurements will be imputed as Grade 0.

- *For fever, if there are missing values and/or non-missing values of temperature from day 1 to day 7 post vaccination which are not qualifying fever definition per protocol for GSK intensity and Chinese intensity tables, then that subject would not be considered for 'Any' rows of the solicited event summary tables.*
- When a specific solicited event is marked as having occurred following a specific study dose (i.e. SDTM CE.CEOCCUR=Y for the specified post-dose period for the event in question), any missing daily recordings will be given imputed values to allow them to contribute to the 'Any' rows but not to specific grade rows of the solicited event summary tables.
- The following table shows how participants contribute to each category for a specific solicited adverse event over the Day X to Day Y post-dose period:

Solicited adverse event category	Participants included in the calculation of the numerator
Any	All participants with at least one occurrence of the adverse event at grade 1, 2, or 3 for table by GSK intensity scale and at grade 1, 2, 3 or 4 for table by Chinese intensity scale between Day X and Day Y or with the adverse event marked as present and at least one missing daily recording between Day X and Day Y
Grade 1	All participants with at least one occurrence of the adverse event at grade 1 between Day X and Day Y
Grade 2	All participants with at least one occurrence of the adverse event at grade 2 between Day X and Day Y
At least grade 3	All participants with at least grade 3 or grade 4

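### The vomiting intensity scale gives no grade to exactly 6 episodes in 24 hours, and neither document says how such a diary day is graded or tabulated

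*SAP*

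**What the plan says.** SAP section 9.2.3, Table 3, grades vomiting as follows:

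- Grade 1: "1-2 times/24 h and do not influence activities"
- Grade 2: "3-5 times/24 h or activities restricted"
- Grade 3: ">6 times within 24 h or require intravenous fluid infusion"
- Grade 4: "Due to hypotension, require hospitalization or nutrition by other routes"

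Protocol section 12.5.8.2.2, Table 26, has the same cut-offs, with grade 3 starting at ">6 times within 24 h". Neither document has a rule for six episodes.

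SAP section 10.1.2.3.2 fixes how a solicited event enters the tables. The *Any* numerator is "All participants with at least one occurrence of the adverse event at grade 1, 2, or 3 for table by GSK intensity scale" (grades 1 to 4 for the Chinese-scale table), plus subjects whose event is marked present with at least one missing day. For an event marked present, "any missing daily recordings will be given imputed values to allow them to contribute to the 'Any' rows but not to specific grade rows". Denominators rest on the Yes/No answer, not on the grade. SAP section 10.1.3.4 computes solicited-event duration by summing the days at grade 1 or above.

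SAP section 8 records a comparable boundary change on the Chinese scale: "Grade 3 for redness/swelling will be defined as redness/swelling with diameter" of 100 mm or more. The protocol had grade 2 below 100 mm and grade 3 above 100 mm.

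**The concern.** Occurrence and intensity of each solicited general adverse event within 7 days of each dose are secondary endpoints (Protocol section 4; SAP section 2). Vomiting intensity is presented separately under the Chinese guideline, and it also feeds the GSK composite of gastrointestinal symptoms. A scale with a hole at the boundary between grades 2 and 3 leaves the grade to whoever records or programs it, in rows where counts may be small.

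The hole looks unintended. The diarrhoea scale, also count-based, runs without a gap from 3-4 to 5-7 to more than 7. SAP Amendment 1 closed the same kind of hole at 100 mm for redness and swelling, but left the vomiting one in place.

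**Working it through.** The plan states no figure to reproduce. The check applies the written criteria to each possible count and then follows the result through the table rules.

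**Inputs.** The four vomiting criteria (SAP Table 3, matching Protocol Table 26), the row rules (SAP 10.1.2.3.2), the duration rule (SAP 10.1.3.4) and the composite rule (SAP 9.2.3). Assumption: where several criteria are met on one day, the highest grade applies.

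**Step 1: grade by count alone.**

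| Episodes in 24 h | Grade |
|---|---|
| 0 | 0 |
| 1-2 | 1 |
| 3-5 | 2 |
| 6 | none |
| 7 or more | 3 |

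Six is the only positive count without a grade.

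**Step 2: six episodes with the other criteria.** Restricted activities give grade 2, needing intravenous fluid gives grade 3, and a grade 4 criterion gives grade 4. The day is ungraded only when none of these applies.

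**Step 3: table rows for an ungraded six-episode day with vomiting marked present, no other day graded and no other day missing.** The plan does not say whether a recorded but ungradable day counts as a missing recording, so both readings are shown.

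| | Treated as missing | Not treated as missing |
|---|---|---|
| Denominator | in | in |
| *Any* | in | out |
| Grade 1, grade 2, at least grade 3, grade 4 | out | out |

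Another vomiting day with grade 1 or higher in the same period would put the subject in *Any* under either reading.

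**Step 4: duration.** An ungraded day is not at grade 1 or above, so it adds nothing to the sum.

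**Step 5: GSK composite.** The grade is the maximum over nausea, vomiting, diarrhoea and abdominal pain. The gap matters there only if no other component sets the grade.

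**Step 6: if the diary collects a chosen grade.** Steps 3 and 4 then do not arise. The subject enters a grade, probably 2 or 3, and is counted in *Any* and in duration. The grade row depends on how that person read the scale.

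**The case against.** The strongest reply is that no ungraded day may ever occur. The intensity tables ask for a raw measurement only for redness, swelling and temperature. SAP section 9.2.3 notes that the diary card does not let the subject choose grade 4 for redness or swelling, which suggests that grades are chosen on the card for other symptoms. The SAP contains no derivation of a vomiting grade from counts. If the grade is chosen, the redness/swelling precedent carries over only in part: that correction works because grades are scored from recorded millimetres, whereas a SAP edit would regrade no vomiting entry. First visits at the listed centres ran from May to September 2021 and SAP Amendment 1 is dated May 2023, so entries had already been made. This stands. It turns the problem into inconsistent recording and limits what a SAP change can repair, but it does not supply a rule for six episodes.

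It is also fair that the ungraded case is narrow, and that six episodes with restricted activities being grade 2 is simply the scale as written.

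A reader might infer that such a subject vanishes from every row of the tables. The documents do not support that: the denominator follows the Yes/No answer, and the subject stays in *Any* if the day is treated as missing or another day is graded. Only the loss from the grade-specific rows is certain for that day, and only if grades are derived from counts.

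**Conclusion.** The scale is not contiguous in either document, and this is a real, minor defect in a stated rule. Its consequence depends on something the documents do not show: whether the diary captures a count or a chosen grade. With counts, an otherwise unqualified six-episode day leaves the grade rows and duration, and its place in *Any* is undefined. With chosen grades, the same event may be recorded as 2 or 3.

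The size cannot be computed because neither document gives a distribution of episode counts; few subjects are likely to be affected. The endpoint is descriptive and the primary efficacy analysis is not involved.

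Two stronger readings are tempting but unsupported. One is that the gap can only understate severity. That presumes grade 3 is correct for six episodes, which neither document says; a recorder could equally enter grade 3, and widening grade 2 to 3-6 would close the gap as well. The other is that the effect falls mainly on the RZV arm. Neither document gives vomiting rates by arm, so the balance is unknown.

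**What to change.** 1. Assign six episodes to one grade, identically in Protocol Table 26, the diary wording and SAP Table 3. Grade 3 as six or more would parallel the 100 mm correction; the sponsor should confirm the choice against the source scale first.
2. List the change in SAP section 8 beside the redness/swelling entry.
3. Before unblinding, state whether the vomiting grade is derived or chosen on the card. State also how any ungradable or already recorded six-episode day enters *Any*, the grade rows and duration. If grades were chosen, say that existing entries stand as recorded unless counts are available in source.

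The cost is a boundary change in two tables, matching diary wording and a few lines in the SAP. If six becomes grade 3, the grade 3 count may rise slightly. A SAP edit alone may not regrade entries already made.
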